Document: PPD

Author: PPD

Version Number:

V2.2

Version Date:

21 March 2018

Template No: CS_TP_BS016 – Revision 3

Reference: CS_WI_BS005

Effective Date: 01May2012

Copyright © 2012 Quintiles Transnational Corp. All rights reserved.

The contents of this document are confidential and proprietary to Quintiles Transnational Corp. Unauthorized use, disclosure or reproduction is strictly prohibited.

In the patient listings all the additional ECG data have to be presented as soon as the first one.

- Spleen: Evaluation Date (to be reported only in the patient’s data listings), Imaging Technique (i.e. MRI, CT scan), Results Interpretation (Normal/Abnormal and Not clinically significant/Abnormal and Clinically Significant) and value of the following parameters:
 - o Longitudinal Diameter (cm);
 - o Antero-Posterior Diameter (cm);
 - o Transversal Diameter (cm);
 - o Splenic Volume Index (SVI, in cm³).

Notably, patients with splenomegaly performed the spleen evaluation as per site-specific clinical practice. Therefore, patients with splenomegaly before the treatment start are followed according to institutional guidelines (i.e. MRI, CT scan). The same imaging technique and the same instrument is used on a patient throughout the Study, *when possible*. No spleen evaluation is performed in splenectomised patients.

- Molecular Examination: Sample Collection Date (to be reported only in the patient’s data listings), Sample Accession Number (to be reported only in the patient’s data listings), Back-Up Sample Collection Date (to be reported only in the patient’s data listings), Back-Up Sample Accession Number (to be reported only in the patient’s data listings) and value of the following parameters:
 - o Positivity (Yes/No);
 - o Qualitative Evaluation (Homozygous/Heterozygous);
 - o Quantitative Evaluation (%).
- MPN-SAF Quality of Life Questionnaire: Completion Date (to be reported only in the patient’s data listings) and value (from a score 0 to a score 10) of the following parameters:
 - o Level of fatigue right NOW (i.e. at the completion of the MPN-SAF questionnaire);
 - o USUAL level of fatigue during past 24 hours (i.e. 24 hours before the completion of the MPN-SAF questionnaire);
 - o WORST level of fatigue during past 24 hours (i.e. 24 hours before the completion of the MPN-SAF questionnaire);
 - o Fatigue has interfered with General Activity during the past 24 hours (i.e. 24 hours before the completion of the MPN-SAF questionnaire);

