 - Incidence of TEAEs leading to dose modification by primary SOC and PT.

In addition, the following primary parameter will be evaluated in **Part A** based on MTD analysis set population:

- MTD of Givinostat.

All outputs for safety outcomes will be based on the SAF analysis set, and presented by DLs (**Part A** only). There will be no planned statistical comparisons among treatment groups for safety data.

ADVERSE EVENTS

AE Investigator terms will be assigned to a PT and will be classified by primary SOC. AEs will be coded using the 20.1 version of MedDRA dictionary. TEAEs are defined as adverse events started at or after the first administration of study treatment.

See [Appendix 2](#) for handling of partial dates for AEs. In the case where it is not possible to define an AE as treatment emergent or not, the AE will be classified by the worst case (i.e. TEAE).

An overall summary of number of patients within each of the categories described in the sub-section below, will be provided as specified in the templates. Listings will include AEs and TEAEs.

A case narrative for each AE leading to treatment discontinuation (the “Action Taken with Study Drug” in section “AE” of the electronic CRF is “Definitively withdrawn”), and/or leading to death (see below), and/or ongoing at the end of treatment (the “Outcome” in the section “AE” of the electronic CRF is “Ongoing” at the time of database look) will be reported in the Clinical Study Report.

ALL TEAEs

Document PPD

Author: PPD

Version Number:

V2.2

Version Date:

21 March 2018

Template No: CS_TP_BS016 – Revision 3

Reference: CS_WI_BS005

Effective Date: 01May2012

Copyright © 2012 Quintiles Transnational Corp. All rights reserved.

The contents of this document are confidential and proprietary to Quintiles Transnational Corp. Unauthorized use, disclosure or reproduction is strictly prohibited.

Incidence of TEAEs will be presented by primary SOC and PT and also broken down further by maximum severity and relationship to Study medication.

SEVERITY AND COMMON TERMINOLOGY CRITERIA FOR ADVERSE EVENTS

AEs will be graded by the Investigators according to the Common Terminology Criteria for Adverse Events (CTCAE) version 4.03, dated 14th June 2010. The grade assigned by the Investigator will be used for this analysis.

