19. EXPLORATORY OUTCOMES

19.1. PARTS A AND B

The following exploratory parameters will be evaluated using ad-hoc descriptive analysis in **Parts A and B** based on ITT analysis set and PP analysis set:

- The effect of Givinostat on each single response parameter according to the clinico-haematological ELN (for PV and ET) [1] and EUMNET response criteria (for MF) [7]; note that only in case the enrolment in Part A is slow (i.e. < 5 patients enrolled in 3 months), the eligibility for this part of the study could be expanded to all patients with cMPN.
- Effects of Givinostat on PD markers.
- Effects of Givinostat on spleen size in patients with confirmed splenomegaly at baseline.
- Improvement of constitutional symptoms evaluated according to MPN-SAF QOL questionnaire [8, 9] including patients without the symptom of headache, pruritus and microvascular symptoms (i.e MPN SAF Score =0) and number and percentage of patient with symptom score from 0 to 3; from 4 to 6 and more than 7.

Document: PPD

Author: PPD

Version Number:

V2.2

Version Date:

21 March 2018

Template No: CS_TP_BS016 – Revision 3

Reference: CS_WI_BS005

Effective Date: 01May2012

Copyright © 2012 Quintiles Transnational Corp. All rights reserved.

The contents of this document are confidential and proprietary to Quintiles Transnational Corp. Unauthorized use, disclosure or reproduction is strictly prohibited.

- Reduction of the JAK2V617F allele burden, tested by quantitative RT-PCR.
- Reduction of the symptomatic treatment of pruritus in term of dosage and/or days of treatment.

The following exploratory parameters will be evaluated using ad-hoc descriptive analysis in Part B based on ITT analysis set and PP analysis set:

- The preliminary efficacy of Givinostat after 6 cycles of treatment according to the “new” ELN criteria (i.e. revised ELN response criteria) [2]. In all cases, the medical judgment of the Investigator’s is taken into account. In particular, if the Investigator’s clinical response assessment – that takes into account the overall medical judgment of the specific patient’s case - is not in agreement with the exact application of the revised clinico-haematological ELN response criteria , the Investigator’s assessment will supersede the “mathematical” application of these criteria and used for analysis into study report. Also mathematical application of ELN response criteria (not agreed by the medical site team) will be analyzed.

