- High: Above the upper limit of the laboratory reference range.

Potentially clinically significant laboratory values will be summarised by laboratory variable. Platelets values will be evaluated as a potentially clinically significant low value at any time during the study, and will be presented by visit.

Document: PPD

Author: PPD

Version Number:
Version Date:

V2.2
21 March 2018

Template No: CS_TP_BS016 – Revision 3
Effective Date: 01May2012

Reference: CS_WI_BS005

The Platelets potentially clinically significant low value is defined as follows:

- Platelets count $< 150 \times 10^9/L$ but $> 75 \times 10^9/L$ (i.e. grade 1 thrombocytopenia as per CTCAE version 4.03);
- Platelets count $< 75 \times 10^9/L$ but $> 50 \times 10^9/L$ (i.e. grade 2 thrombocytopenia as per CTCAE version 4.03);
- Platelets count $< 50 \times 10^9/L$ but $> 20 \times 10^9/L$ (i.e. grade 3 thrombocytopenia as per CTCAE version 4.03);
- Platelets count $< 25 \times 10^9/L$ (i.e. grade 4 thrombocytopenia as per CTCAE version 4.03).

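### The platelet bands in SAP section 20.2 overlap between 20 and 25 and skip 50 and 75, and the symptom bands in section 19.1 skip a score of 7: a minor tabulation fix

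*SAP*

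**What the plan says.** SAP section 20.2 gives four platelet bands, each tied to a CTCAE version 4.03 grade. Grade 1 lies between 75 and 150 and grade 2 between 50 and 75 (x10^9/L), with strict inequalities at both ends. The grade 3 line reads "Platelets count $< 50 \times 10^9/L$ but $> 20 \times 10^9/L$ (i.e. grade 3 thrombocytopenia as per CTCAE version 4.03". The last line has an upper limit only: "Platelets count $< 25 \times 10^9/L$ (i.e. grade 4 thrombocytopenia as per CTCAE version 4.03".

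Their use is stated earlier in the same section: "Platelets values will be evaluated as a potentially clinically significant low value at any time during the study, and will be presented by visit". Section 20.1 also asks for a listing of markedly abnormal values and uses grade 3 thrombocytopenia as its example, so the same limits may feed that listing.

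Section 19.1, on exploratory outcomes, asks for the "number and percentage of patient with symptom score from 0 to 3; from 4 to 6 and more than 7" in connection with headache, pruritus and microvascular symptoms. Section 10 gives the scale of the questionnaire items: "value (from a score 0 to a score 10) of the following parameters".

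The SAP has no rule for which grade takes precedence where two apply. It also does not say where a platelet count of 50 or 75, or a score of 7, should go.

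**The concern.** A frequency table by category needs bands that do not overlap and that together cover every value of interest. Neither set does this.

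In the platelet set, the grade 3 lower limit (20) contradicts the grade 4 limit (25) on the next line. This is visible inside the SAP, without recourse to CTCAE. In the symptom set, the top band starts one point too late.

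A programmer who follows the text literally would count some patients twice and leave others out. One who repairs it silently applies an undocumented rule, and two programmers could report different grade 3 counts from the same data. Platelets deserve care here: they are the one laboratory variable for which section 20.2 writes out such bands, and section 3.7 records the observed platelet decrease among the reasons for the choice of Part B dose. The platelet overlap also sits at the grade 3/4 boundary, the most serious one in the table. In the symptom table, a patient who improves from 8 to 7 or worsens from 6 to 7 would leave the bands.

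**Working it through.** There is no stated figure to reproduce; the check is whether each possible value falls in exactly one band.

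**Platelets (x10^9/L), limits from section 20.2 exactly as written**

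| Grade | Band |
|---|---|
| 1 | 75 < x < 150 |
| 2 | 50 < x < 75 |
| 3 | 20 < x < 50 |
| 4 | x < 25 |

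Number of bands met by each whole number from 0 to 149:

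- Two bands: 21, 22, 23, 24. In general this is the intersection of (20, 50) with values below 25, the open interval (20, 25). In half-unit steps it holds 20.5 to 24.5.
- No band: 50 and 75.
- One band: all others. Exactly 20 is grade 4 only (it is not above 20), and exactly 25 is grade 3 only (it is not below 25).

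At 75 and 50 the lower limit of one band equals the upper limit of the next. At the last boundary the pair is 20 and 25, which breaks that pattern.

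**Symptom score, bands from section 19.1, scale 0 to 10 from section 10** (assuming whole-number item scores)

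- 0, 1, 2, 3: first band.
- 4, 5, 6: second band.
- 7: no band.
- 8, 9, 10: top band.

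One of the 11 possible scores is unassigned.

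**Size per case.** Section 4 plans the final analysis on 28 Part B patients, so one misplaced patient is 1/28 = 0.036, or 3.6 percentage points. By default, Appendix 1 takes the whole analysis population as denominator. A patient with a count of 50 or 75, or a score of 7, therefore stays in the denominator without entering any band.

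**Check of possible repairs**

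- Changing only 20 to 25 and keeping strict limits: no overlap, but 25, 50 and 75 are then in no band.
- Changing 20 to 25 and making lower limits inclusive (75 ≤ x < 150; 50 ≤ x < 75; 25 ≤ x < 50; x < 25): every value from 0 to 149 is in exactly one band.
- Starting the top symptom band at 7: every score from 0 to 10 is in exactly one band.

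**The case against.** A reader might infer more than the SAP supports. Grade 4 haematological toxicity is a DLT criterion (section 3.2.1) and thrombocytopenia was part of the Part B dose discussion, so the faulty bands might seem to put the DLT count or the MTD in doubt. They do not:

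- For adverse event severity, section 17.1 says "The grade assigned by the Investigator will be used for this analysis".
- The same section identifies DLTs from a dedicated question in the electronic CRF, not from laboratory bands.
- Section 3.7 dates the study team's MTD decision to July 2015; this SAP version is dated 21 March 2018.
- ELN response (section 16.3) uses its own platelet limit of 400 x10^9/L and the absence of symptoms, so neither it nor the Simon rule uses these bands.

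A second stronger reading is that patients are lost from the analysis. They are not. Platelet values are also reported as actual values, changes from baseline, shifts and listings (section 20.1). Exploratory parameters also get summary statistics and changes from baseline (section 19.1). Only a row in a frequency table is wrong.

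Three further points stand. The harm is conditional: it needs a patient with one of the affected values, and the SAP gives no basis for how often that occurs. Band percentages that fall short of 100% are not themselves proof of error, because missing assessments do the same under the default denominator. The table templates that accompany the SAP (section 8) are not available here, so the programmed categories may already differ from the text.

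It can also be said that 20 is an obvious slip, since each line refers to CTCAE. That makes the repair easy, but the written rule remains contradictory. The symptom gap is unlikely to be a text-extraction fault, because the version history entry for V2.1 shows the same three bands.

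**Conclusion.** The defect is real and small. As written, platelet counts strictly between 20 and 25 x10^9/L meet two grades, counts of exactly 50 or 75 meet none, and a symptom score of 7 has no band.

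The effect is confined to the descriptive by-visit platelet table, any listing that uses these grades, and the exploratory symptom table. It is 3.6 percentage points per affected patient if all 28 Part B patients form the denominator. It would be larger in a smaller analysis set or in a Part A dose-level column, and zero if no patient has such a value. The conclusion assumes that outputs follow the SAP text and that symptom items are scored in whole numbers.

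No primary or secondary endpoint, decision rule, DLT or Investigator grade depends on either set of bands. This is a minor correction.

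**What to change.** For tabulation only, reconcile the grade 3 lower limit in section 20.2 with the SAP's own grade 4 limit and make every lower limit inclusive:

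- Grade 1: below 150 and at least 75
- Grade 2: below 75 and at least 50
- Grade 3: below 50 and at least 25
- Grade 4: below 25

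Since the lines cite CTCAE version 4.03, check the final limits against that source when editing. Changing 20 to 25 alone is not enough, as the cut-points would still be unassigned.

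In section 19.1, make the top symptom band 7 or more. A separate band for 0 is not needed, because the section already counts symptom-free patients on their own.

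The cost is a few words in two sections, a check that the table templates match, and a re-run of the affected tables, listings and figures. No dosing or other clinical rule is touched.

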3.4. TREATMENTS

3.4.1. TREATMENTS ADMINISTERED

Givinostat is supplied by the Sponsor or its designee as hard gelatine capsules for oral administration at the strength of 50 mg, and/or 75 mg, and/or 100 mg each.

Each capsule contains a granulate (obtained by wet granulation) composed of ITF2357, sodium starch glycolate, hydroxypropyl methyl cellulose (HPMC), sodium lauryl sulphate, lactose, magnesium stearate and colloidal silica.

The packaging consists of HDPE plastic bottles- closed with a PP screw cap, tamper evident - containing hard gelatine capsules of Givinostat. Each bottle contains:

- 30 capsules of 50 mg of Givinostat, or
- 30 capsules of 75 mg of Givinostat, or
- 15 capsules of 100 mg of Givinostat.

At each visit, patients receive a number of bottles sufficient to cover the period between two visits.

In **Part A** patients can be treated in DLs at the following starting daily doses of Givinostat:

Document: PPD

Author: PPD

Version Number:

V2.2

Version Date:

21 March 2018

Template No: CS_TP_BS016 – Revision 3

Reference: CS_WI_BS005

Effective Date: 01May2012

Copyright © 2012 Quintiles Transnational Corp. All rights reserved.

The contents of this document are confidential and proprietary to Quintiles Transnational Corp. Unauthorized use, disclosure or reproduction is strictly prohibited.

- 50 mg b.i.d.;
- 100 mg b.i.d.;
- 150 mg b.i.d.;
- 200 mg b.i.d.;
- 150 mg t.i.d.;
- 200 mg t.i.d..

Intermediate Dose Levels (IDLs) and, consequently, additional DLs can be used to establish the MTD (for more details, see [paragraph 4.1.1.3](#) of the Study protocol version 3.0).

Notably, the tested DLs to be considered for the MTD statistical analysis, are resumed in the **Table 1.1**.

Table 1.1 - Dose escalation of Givinostat performed in Part A

Givinostat daily dose	Givinostat dose level (DL)	DL used primarily to asses	Label for Tables, Listings and Figures (TLFs)
100 mg b.i.d.	DL1 (first three patients)	MTD, PK, PD	DL1
	DL1 (additional three patients)		DL1 expanded
2 capsules of 50 mg at the morning AND 1 capsule of 50 mg at the evening (i.e. 12 hours after)	DL6	MTD, PK, PD	DL6
50 mg b.i.d.	DL0	Safety, PK, PD*	DL0

* DL previously demonstrated as safe.

No patient will be treated at the DL2, none at DL3, none at DL4, none at DL5 in **Part A**, as per dose escalation scheme describe in the Study protocol and also summarised in the [section 3.2.2.1](#). of the present document.

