20. OTHER SAFETY OUTCOMES

All patients who receive at least one dose will be included in the safety evaluation.

Safety data including laboratory evaluations, physical exams, ECG monitoring and vital signs assessments will be summarised at each time point.

Descriptive statistics (arithmetic mean, standard deviation, median, minimum and maximum) will be calculated for quantitative safety data as well as for the difference from baseline, *if applicable*. Frequency counts will be compiled for classification of qualitative safety data.

In addition, a shift table describing out of normal range shifts (low/normal/high values) will be provided for clinical laboratory results.

A normal-abnormal shift table will also be presented for physical exam and ECG results.

20.1. LABORATORY EVALUATIONS.

Results from the local laboratories will be included in the reporting of this study for Haematology,

Document PPD

Author: PPD

Version Number:

V2.2

Version Date:

21 March 2018

Template No: CS_TP_BS016 – Revision 3

Reference: CS_WI_BS005

Effective Date: 01May2012

Copyright © 2012 Quintiles Transnational Corp. All rights reserved.

The contents of this document are confidential and proprietary to Quintiles Transnational Corp. Unauthorized use, disclosure or reproduction is strictly prohibited.

Blood Chemistry and Urinalysis.

A list of laboratory assessments to be included in the outputs is included in the [paragraph 4.7.1](#) of the Study protocol.

Outputs will be based on the SAF analysis set, presented by DL (for **Part A only**), and will use the International System (SI) Units.

The following summaries will be provided for Haematology, Blood Chemistry, Urinalysis laboratory data by DL (for **Part A only**):

- Actual and change from baseline by visit (for quantitative measurements);
- Shift from baseline according to normal range criteria (for categorical measurements);
- Presence/absence, with number (n) and percentage (%), where applicable (i.e. Glucose and Protein, for Urinalysis test).
- Listing of laboratory data by Study Part and patient ID;
- Listing of patients with clinically significant abnormal values, as reported in electronic CRF based on Investigator’s judgment;
- Listing of patients with markedly significant abnormal values (e.g. grade 3 thrombocytopenia as per CTCAE version 4.03).

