- For titles and column labels, capitalize important words, i.e. nouns, pronouns, verbs, adverbs and adjectives but not articles, conjunctions or prepositions.
- All Footnotes will be in sentence case format.
- All symbols used in body of outputs will be footnoted.
- Continuous Variables:
 - Number (“n”),
 - Mean,
 - Standard Deviation (“SD”),
 - Median,
 - Minimum (“min”),
 - Maximum (“max”)

will be presented for all variables on the original scale.

- Categorical Variables:
 - Number (“n”),
 - Percentage (%)

in each category will be the default summary presentation.

- The percentage of patients in each category relative to the total number of patients in the relevant analysis population will be the default. Percentages relative to the total number of patients in the relevant analysis population with a non-missing assessment will be specified in a programming note on the shell if required.
- Where percentages are presented, a footnote will be added to explain what the denominator of the percentage is, in the form “Percentages are calculated relative to the total number of patients in the SAF” as the first footnote.
- All computed percentages will be presented using one decimal place except for where the percentage is 100 where no decimal places are presented.
- The percentage will be also presented if the count is zero.

Document: PPD

Author: PPD

Version Number:

V2.2

Version Date:

21 March 2018

Template No: CS_TP_BS016 – Revision 3

Reference: CS_WI_BS005

Effective Date: 01May2012

Copyright © 2012 Quintiles Transnational Corp. All rights reserved.

The contents of this document are confidential and proprietary to Quintiles Transnational Corp. Unauthorized use, disclosure or reproduction is strictly prohibited.

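### The platelet grade bands in SAP 20.2 overlap between grades 3 and 4 and leave counts of exactly 50 and exactly 75 x10^9/L ungraded

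*SAP*

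**What the plan says.** Section 20.2 of the SAP, under the laboratory reference ranges and markedly abnormal criteria, singles out platelets and commits to a display: "Platelets values will be evaluated as a potentially clinically significant low value at any time during the study, and will be presented by visit". It then prints four bands, each tied to the same CTCAE version:

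- Grade 1: "Platelets count $< 150 \times 10^9/L$ but $> 75 \times 10^9/L$ (i.e. grade 1 thrombocytopenia as per CTCAE version 4.03"
- Grade 2: "Platelets count $< 75 \times 10^9/L$ but $> 50 \times 10^9/L$ (i.e. grade 2 thrombocytopenia as per CTCAE version 4.03"
- Grade 3: "Platelets count $< 50 \times 10^9/L$ but $> 20 \times 10^9/L$ (i.e. grade 3 thrombocytopenia as per CTCAE version 4.03"
- Grade 4: "Platelets count $< 25 \times 10^9/L$ (i.e. grade 4 thrombocytopenia as per CTCAE version 4.03"

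Section 20.1 separately plans an output described as "Listing of patients with markedly significant abnormal values (e.g. grade 3 thrombocytopenia as per CTCAE version 4.03". It names the CTCAE version but does not say whether it uses the 20.2 bands.

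On denominators, Appendix 1 states: "The percentage of patients in each category relative to the total number of patients in the relevant analysis population will be the default".

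**The concern.** A grading rule has to give one answer for each value. This one gives two answers over one interval and none at two points, and the SAP has no tie-break or default for either.

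The overlap lies between the two most severe grades. Platelets are also the only laboratory variable for which 20.2 writes out such limits. Section 3.7 cites the observed fall in platelets, and thrombocytopenia as a known side-effect, among the reasons for taking 100 mg b.i.d. as the MTD. Readers of the report will look at this display. As written, it could count one patient in two grades at the same visit, report a count of 22 as grade 3 only, or omit a patient whose count sits on a limit.

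**Working it through.** **Inputs.** The four bands in SAP 20.2, with x the platelet count in x10^9/L:

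| Grade | Printed rule | Whole-number counts that meet it |
|---|---|---|
| 1 | 75 < x < 150 | 76 to 149: 74 counts |
| 2 | 50 < x < 75 | 51 to 74: 24 counts |
| 3 | 20 < x < 50 | 21 to 49: 29 counts |
| 4 | x < 25 | 0 to 24: 25 counts |

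The SAP states no figure on this point to reproduce, so the check is to apply the printed rule to every whole-number count from 0 to 149.

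**Overlap.** Grades 3 and 4 both hold when 20 < x < 25, that is for 21, 22, 23 and 24. Non-integer values such as 20.5 and 24.9 also meet both. Exactly 20 is grade 4 only and exactly 25 is grade 3 only.

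**Gaps.** x = 75 fails both x > 75 and x < 75. x = 50 fails both x > 50 and x < 50. Neither value meets any grade.

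**Cross-check.** The bands give 74 + 24 + 29 + 25 = 152 memberships for 150 counts. With four counts in two bands, two in none and 144 in one, the total is 144 + 4 × 2 = 152, which agrees.

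**Share of each band in the overlap.** 4/29 = 13.8% of the whole-number values in the printed grade 3 band, and 4/25 = 16.0% of those in grade 4. These describe the width of the defect on the scale. They are not expected proportions of patients.

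**What literal programming gives.**

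- Separate flags: a count of 22 is tallied in grade 3 and in grade 4.
- An if/else chain in printed order: 22 stops at grade 3, so grade 4 catches only counts of 20 or less.
- An if/else chain from the most severe grade down: 22 becomes grade 4.
- In all three, counts of 50 and 75 are left out.

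**Effect of one patient.** With the Appendix 1 denominator, one patient is:

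- 1/28 = 3.6 points with the full Part B sample;
- 1/12 = 8.3 points at Stage 1;
- 1/3 = 33.3 points in a three-patient Part A column, such as the one Table 1.1 in section 3.4.1 labels "DL1 (first three patients".

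**Candidate corrections.** With grade 1 as 75 ≤ x < 150, grade 2 as 50 ≤ x < 75, grade 3 as 25 ≤ x < 50 and grade 4 as x < 25, every whole-number count from 0 to 149 falls in exactly one grade. Changing 20 to 25 while keeping strict limits removes the overlap but leaves 25, 50 and 75 ungraded. Both changes are needed.

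**The case against.** The strongest reply is that this is a one-digit slip whose intent can be read from the list. The other adjacent bands share a limit (75 and 50), grade 4 is printed as below 25, and every line names the same CTCAE version, so a sensible programmer would use 25 as the grade 3 floor. That is a fair reading of the intent. It does not make the printed rule right, and it asks the programmer to depart silently from the SAP.

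A second reply is that no patient disappears from safety reporting. This is correct. Sections 20 and 20.1 also plan values and changes by visit, low/normal/high shift tables and full laboratory listings. Section 17.1 uses the investigator's grade for AEs. The defect is confined to the platelet-band display, and to the 20.1 listing only if that listing borrows these bands.

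Third, the percentage-point figures are simply one over the sample size and would describe any single misclassification. That is also true. The three-patient illustration has a further limit. Section 3.2.1 makes drug-related grade 4 haematological toxicity a DLT, and section 3.7 reports one Cycle 1 DLT among the six DL1 patients, which was dyspepsia. A drug-related grade 4 count in DL1 during Cycle 1 is therefore excluded by the SAP's own account. Later cycles, other dose levels, and counts of exactly 50 or 75 are not.

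Finally, a greater-than-or-equal sign could have been lost when the text was read from PDF, which would close the gaps at 50 and 75. The sign survives elsewhere in the SAP, for instance in the spleen-volume criterion of section 20.4. The mismatch of 20 against 25 would remain in any case.

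**Conclusion.** The concern holds. Followed literally, the 20.2 bands assign two grades to any count above 20 and below 25 x10^9/L and no grade to exactly 50 or exactly 75. That is four doubly graded and two ungraded values among the 150 whole-number counts from 0 to 149.

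The effect on the report depends on how many patients have such counts at a visit. The SAP does not give this, and it may be none. The reach is one descriptive safety display and, conditionally, one listing. The primary safety analysis by AE, the DLTs, the MTD and the efficacy endpoints do not depend on these bands. The correction should still be made, because the ambiguity sits at the grade 3/4 boundary of the one laboratory variable that 20.2 grades explicitly.

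**What to change.** Replace the four lines in section 20.2 with bands whose lower limits are inclusive (x10^9/L):

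- Grade 1: below 150 and at least 75
- Grade 2: below 75 and at least 50
- Grade 3: below 50 and at least 25
- Grade 4: below 25

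State that the same bands drive the platelet entries in the 20.1 listing of markedly abnormal values.

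The cost is an edit to one list and to the matching derivation code, with no new data.

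Optionally, and only if the output templates do not already include it, a table of each patient's lowest post-baseline platelet grade would cover the any-time part of the 20.2 commitment. It would use scheduled and unscheduled values, to C3D28 and over the whole treatment period, and needs one derived variable. The band correction does not depend on it.
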